1. INTRODUCTION AND STUDY RATIONAL

1.1. INTRODUCTION

According to the INVS (National Institute of Health Surveillance), 54,000 women develop breast cancer each year [1] and their survival rate at 5 years is today of 86% [2]. One of the most common complications of breast cancer treatment is lymphedema, and despite progress made in surgery, 20% of them will progressively develop chronic lymphedema [3], corresponding to 10,800 new cases of arm lymphedema per year.

The impact of arm lymphedema on women is often important because it increases their anxiety, induces alterations of their body image and in their quality of life [4-6]. Over time, it can cause a real functional disability and pain [6,7].

Currently, there is no known surgical or pharmacological cure for lymphedema [8]. The treatment of lymphedema relies mainly on the physical treatments prescribed to reduce and maintain the size of the arm, restore the motor functions, improve its appearance and reduce pain [8]. It is based on decongestive therapy that combines an initial reduction phase with intensive decongestive treatment followed by a maintenance treatment [9,10]. According to the recommendations of French national health authority [11] and international consensus [12], the reduction must be done through relatively or totally non-elastic bandages and the maintenance phase by compression sleeves and / or the continuation of the bandages.

A prospective cohort study of 682 women with lymphedema in relation to breast cancers studied the maintenance of arm volume after the intensive reduction phase. It shows a gradual reappearance of lymphedema in the first year in 38.1% of women and demonstrates that women who wore a compression sleeve and compression bandages at night have a significantly reduced risk of relapse of 50% [hazard ratio, 0.53, (0.34-0.82), P = 0.004] [13].

1.2. RATIONAL

One of the difficulties encountered in the treatment of lymphedema, both in the active reduction phase and in the maintenance phase, is the appliance of the short-length compression bandages which requires good technicality and experience to exert the pressure required to remove liquids from tissue spaces and reduce the volume of the arm or prevent it from increasing again.

During the intensive decongestive treatment phase, which usually takes place in specialized lymphedema treatment departments, the staff are properly trained and have the required experience, but the appliance of these short-length compression bandages requires a lot of time. During the maintenance phase, the appliance of short stretch bandages gives way during the day to the wearing of a compression sleeve which can be put on fairly easily. But during the night, in the absence of a nurse or a spouse with the technical skills required to put them in place, few patients can benefit from the wearing of short stretching bandages. During the maintenance phase, many patients quickly give up these nocturnal bandages, thus losing the gain obtained during the reduction phase [10]. This situation is all the more regrettable that, as shown in the studies, this nocturnal wearing contributes to a very significant reduction in the rate of reappearance of lymphedema and avoids the recurrent need of intensive reduction sessions in hospitals, which are costly for health insurance. and uncomfortable for the patients.

To improve this situation, medi has developed a device called circaid[®], consisting of non-elastic bands adjustable and repositionable with "Velcro" systems, which can be used both for the intensive reduction phase but also during the maintenance phase by the patients themselves because of its ease of placement.

It is composed of several inelastic strips or removable straps, parallel and overlapping slightly to leave no crease and no space between them. Velcro tabs or fasteners help ensure proper initial positioning and readjustment as the arm volume is reduced. This gives a given pressure by tightening or loosening each band while limiting friction and discomfort. In the intensive reduction phase, its ease of use reduces the time devoted by nurses to the use of short stretching tapes which, in addition to the need for good technique, requires a significant amount of time. In the maintenance phase, this original and comfortable compression device allows the patient to become autonomous after minimal learning. The simplicity of the introduction of the system on the limb and the calibration of the delivered pressure allows to develop the self management of the treatment, because it is possible to reposition the bands as and when the decrease of the edema, which makes it possible to optimize the effectiveness of the treatment. The ability to instantly readjust the circaid[®]Juxtafit system allows to constantly apply the right level of pressure delivered, to reduce the volume of the limb. This is not possible with a traditional multilayer bandage if the different layers are not completely remove. A visual calibrator ensures the right level of pressure delivered at all times.

In addition to efficiency, patients' quality of life is improved by being able to remove and return it on their own, making it easier to wash or dress. Similarly, less rigid while being just as compressive, it allows a better comfort in the daily gestures and in particular to have a normal range of arm flexion movements more compatible with driving than the wearing of tapes.

The product is currently marketed in many countries and is reimbursed in the following countries: United States, Quebec, the Netherlands, United Kingdom, Austria in the indication of the treatment of lymphedema. In view of its admission to reimbursement in France, a meeting was held with HAS experts in the context of the so-called early meeting procedure in order to define the study that should be done. A detailed synopsis which is the one of the present protocol has been validated by the methodological experts of the HAS as being able to bring the arguments of effectiveness required by being as close as possible to the usual practice and by covering at the same time the phase of intensive reduction and the maintenance phase. It aims to compare the current protocol of care considered optimal for the reduction of lymphedema and the maintenance of this reduction with the protocol of care which would integrate the device circaid[®] in substitution to the laying of bands with short extension as it is now in other countries.

2. STUDY OBJECTIVES

2.1. PRIMARY OBJECTIVE

The main objective of the study is to compare, at the 30th day of the initial maintenance phase, the reduction in the volume of lymphatic edema of the upper limb obtained under the effect of the wearing of a compression sleeve on the day associated with the night wearing of the system of contention circaid[®] versus the wearing of a compression sleeve during the day associated with a possible treatment with it during the night, according to the recommendations of the HAS.

2.2. SECONDARY OBJECTIVES

The secondary objectives are:

- To compare, on the 5th day of the reduction phase, the reduction in the volume of lymphatic edema of the upper limb obtained under the effect of the night and day wearing of the circaid® compression system and the night and day wearing of short lengthening bands such as recommended by the HAS.
- To compare, at the 90th day of the maintenance phase, the reduction in the volume of lymphatic edema maintained by the wearing of a compression sleeve during the day associated with the circaid® compression system at night and the wearing of a compression sleeve during the day associated with a possible wearing at night.
- To compare, at the 5th day of the reduction phase, at the 30th day of the initial maintenance phase and at the 90th day of the maintenance phase:
 - the physicians' opinions on lymphedema-induced discomfort improvement through the CGII (Clinical Global Improvement Impression);
 - the patients' opinions on lymphedema-induced discomfort improvement through the PGII (Patient Global Improvement Impression).
- To compare, at the 30th day of the initial maintenance phase and at the 90th day of the maintenance phase:
 - the adherence of patients to the wearing of their maintenance treatment;
 - the satisfaction and the wearing comfort experienced by the patients;
 - the patients' opinions on the ease of use of the product: the need for a third party, applications of pressure, the need for nurses or caregivers.
- To compare the tolerance of the different products at different phases of reduction and maintenance.

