4. NATURE OF THE TRIAL

Controlled randomized open label clinical trial on two parallel groups.

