9. STUDY COURSE

Following the meeting with CNEDIMTS (HAS), three observation periods were defined with the following products:

- D1 to D5: intensive hospital treatment performed by the night and day wearing of the circaid® compression system versus the night and day wearing of short stretching tapes.
- B. DD (Day of discharge from the hospital) to DD +30: ambulatory initial maintenance phase carried out by the wearing of a compression sleeve on the day associated with the nighttime compression system circaid® versus wearing a compression sleeve on the day associated with a possible treatment at night, as recommended by HAS.
- C. DD + 31 to DD + 90: ambulatory maintenance phase carried out by the wearing of a compression sleeve on the day associated with the nighttime circaid® compression system versus the wearing of a compression sleeve on the day associated with possible treatment at night.

Study design:

The study therefore includes four medical follow-up visits on day 0 (D0), day 5 (D5) (+/- 1 day), day of discharge (DD) + 30 days (+/- 5 days) and DD + 90 days (+/- 10 days), followed by self-questionnaire during the maintenance phase between DD and DD + 90, DD designating the day of discharge from the hospital at the end of the intensive reduction phase.

At D0, the doctor:

- collects the informed written consent of the patient after having duly informed her;
- collects its socio-demographic characteristics: age, occupation;
- collects the characteristics of its lymphedema: origin, date of onset, stage of edema according to the classification of the international society of lymphology, laterality of edema, volume of the arm with lymphedema, and volume of lymphedema compared to contralateral arm;

- collects the quality of life measured by the Lymph IFC specific questionnaire;
- implements decongestive treatment with the product defined by randomization.

At D5 (+/- 1 day), the doctor:

- collects the characteristics of lymphedema: stage of edema according to the classification of the international society of lymphology, volume of the arm with lymphedema, and volume of lymphedema compared to the contralateral arm;
- completes the PGII and CGII;
- records patient satisfaction in terms of efficiency and comfort of wearing measured on Likert scales in 5 classes;
- collects the occurrence of adverse events and their imputability to the products under study according to the materiovigilance;

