- collects the quality of life measured by the Lymph IFC specific questionnaire;
- gives the patient a self-questionnaire on which she reports each week who has placed the contention device (herself, spouse, nurse), and the existence of an intolerance to the wearing of it;
- gives the patient, according to the randomization list, the products under study during the maintenance phase;
- provides a nursing prescription for the application of a possible treatment to the patients concerned.

At DD + 30 days (+/- 5 days), the doctor:

- collects the characteristics of lymphedema: stage of edema according to the classification of the international society of lymphology, volume of the arm with lymphedema, and volume of lymphedema compared to the contralateral arm;
- collects the PGII and CGII;
- collects the quality of life measured by the Lymph IFC specific questionnaire;
- records patient satisfaction in terms of efficiency and wearing comfort measured on Likert scales in 5 classes;
- collects the observance of the port during the initial maintenance phase by the adapted Morisky score;
- collects the occurrence of adverse events and their imputability to the products under study according to the materiovigilance;
- retrieves the self-questionnaire from the early maintenance period and gives the patient a self-questionnaire for the maintenance period where she reports on each week who apply the compression device (herself, spouse, nurse), and the existence of an intolerance to the wearing of it;
- provides a nursing prescription for the application of a possible treatment to the patients concerned;
- gives the patient, according to the randomization list, the products under study during the maintenance phase.

At DD + 90 days (+/- 10 days), the doctor:

- collects the characteristics of lymphedema: stage of edema according to the classification of the international society of lymphology, volume of the arm with lymphedema, and volume of lymphedema compared to the contralateral arm;
- collects the PGII and CGII;
- collects the quality of life measured by the Lymph IFC specific questionnaire;

- records patient satisfaction in terms of efficiency and wearing comfort measured on Likert scales in 5 classes;
- collects the observance of the port during the long-term maintenance phase by the adapted Morisky score;
- collects the occurrence of adverse events and their imputability to the products under study according to the materiovigilance;

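### The ease-of-use opinion is to be compared at DD+30 and DD+90 but is scheduled only at DD+90; separately, the cost comparison is worded as a within-group test

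*Combined protocol and SAP*

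**What the plan says.** Section 2.2 groups three patient-reported outcomes under one instruction: "To compare, at the 30th day of the initial maintenance phase and at the 90th day of the maintenance phase". They are adherence, satisfaction with wearing comfort, and patients' "opinions on the ease of use of the product: the need for a third party, applications of pressure, the need for nurses or caregivers".

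Section 9 fixes the two outpatient visits at "day of discharge (DD) + 30 days (+/- 5 days) and DD + 90 days (+/- 10 days"). Its DD+30 list covers adherence (the doctor "collects the observance of the port during the initial maintenance phase by the adapted Morisky score") and satisfaction (the doctor "records patient satisfaction in terms of efficiency and wearing comfort measured on Likert scales in 5 classes"). It contains no ease-of-use opinion. The user-friendliness opinion, including third-party help and application of pressure, and a separate item on the need for nurses or carers, are in the DD+90 list only.

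Some related information does reach DD+30. At D5 the patient receives a self-questionnaire on which "she reports each week who has placed the contention device (herself, spouse, nurse"), together with any intolerance. At DD+30 the doctor "retrieves the self-questionnaire from the early maintenance period". Nursing prescriptions are issued at D5 and DD+30 for the patients concerned.

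Section 13.4.3 compares ease-of-use opinions between groups by Chi2 or Fisher tests and names no visit. It also compares the mean number of nurse visits between groups by t-test. It then compares the economic impact of those visits by Student t-tests described as being on repeated series. Section 4 describes the design as a "Controlled randomized open label clinical trial on two parallel groups".

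**The concern.** An objective that names a time point needs data collected at that time point. A site that follows section 9 has no instruction to ask for the ease-of-use opinion at DD+30, and an opinion not recorded then cannot be recovered later. The outcome matters to the sponsor's argument, because section 1.2 rests part of the device's rationale on patient autonomy and on the patient's ability to set the pressure herself.

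The cost wording raises a different question. A test for repeated measurements compares a patient with herself. A trial with two parallel arms needs a test between different patients. If the wording were followed literally, the economic result would not compare the arms.

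**Working it through.** No figure in the plan bears on this point, so the check sets the sections side by side.

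**Step 1: objective against schedule.** Inputs: section 2.2 for what is promised, and the DD+30 and DD+90 lists in section 9 for what is scheduled.

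| Outcome in section 2.2 | Promised at | Scheduled at DD+30 | Scheduled at DD+90 |
|---|---|---|---|
| Adherence | DD+30, DD+90 | Yes | Yes |
| Satisfaction and comfort | DD+30, DD+90 | Yes | Yes |
| Ease-of-use opinion | DD+30, DD+90 | No | Yes |

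Promised: 3 outcomes × 2 visits = 6 comparisons. Scheduled: 2 + 2 + 1 = 5. Missing: 6 − 5 = 1, the ease-of-use opinion at DD+30.

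**Step 2: what DD+30 can supply for the three elements of that outcome.**

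| Element | Listed source by DD+30 | Listed source at DD+90 |
|---|---|---|
| Third party | Weekly form: who placed the device (behaviour) | Opinion item |
| Application of pressure | None | Opinion item |
| Nurses or caregivers | Weekly form (behaviour); nursing prescriptions (care ordered) | Item on need for nurses or carers |

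So at DD+30 no element is collected as an opinion, two have behavioural data, and one has no listed source.

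**Step 3: whether another section resolves it.** Section 8.2 places the ease-of-use opinion and the need for nurses in the maintenance phase and names no visit. Section 13.4.3 names none for the test. Neither section says which of 2.2 and 9 governs.

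**Step 4: the cost test.** The repeated-series phrase occurs four times in section 13.4.3. Three uses (CGII/PGII, and quality of life twice) are explicitly for change within each group. The fourth is economic impact, where no group comparison is stated, although the sentence before it does state one for nurse visits. The two readings are different tests:

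- Paired: t = mean(d) / (s_d / √n), where d is the difference between two measurements on the same patient.
- Independent groups: t = (mean₁ − mean₂) / √(s₁²/n₁ + s₂²/n₂), where the two means come from different patients.

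Each patient belongs to one arm, so the paired form has no between-arm difference to test.

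**Step 5: sources for visits and costs.** The sources listed in section 9 are who placed the device each week, the need for nurses or carers at DD+90, and the nursing prescriptions. None is described as a count of visits made, and no cost source is named. The documents give no visit rate or unit cost, so no effect on those results can be calculated.

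**The case against.** The best defence is that section 2.2, not section 9, is the outlier. Section 8.2 refers only to the maintenance phase, and section 9 separates the initial maintenance phase (to DD+30) from the maintenance phase (DD+31 to DD+90). One collection at DD+90 is compatible with that, and the repair would be a line of wording. This stands as a possible resolution, but the text does not adopt it: section 2.2 names both days.

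On cost, the preceding sentence compares nurse visits between groups, so a drafting or translation slip is plausible. Section 13.2 also defers tests and endpoints to a later analysis plan. That plan can settle the test and the named visit. It cannot supply opinions that sites were not asked to collect.

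Three stronger inferences are not supported:

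- That nothing on third-party or nurse involvement exists at DD+30. The weekly self-questionnaire covers it as behaviour.
- That visit counts and costs will not be collected. The forms were not available for review, the weekly form is known only from a short description, and section 11.1 requires all protocol data to be in the observation book. The most that can be said is that the protocol text names no source.
- That a wrong cost test has been chosen. The wording is ambiguous; it does not prove the intention.

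Nurse-visit numbers and economic impact also appear in neither the objectives of section 2.2 nor the criteria of section 8.2, so they are supplementary analyses.

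**Conclusion.** The mismatch between sections 2.2 and 9 is a firm internal contradiction, limited to one of six promised comparisons: the ease-of-use opinion at DD+30. The gap is complete for the opinion itself and for application of pressure. It is partial for third-party and nurse involvement.

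The cost wording is a smaller but real defect: as written, it does not clearly compare the two arms. The unnamed source for nurse visits and costs is a request for clarification and not a demonstrated omission.

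Only secondary or supplementary analyses are touched. The conclusion assumes that the section 9 visit lists are what sites follow. If the observation book already carries the opinion item at DD+30, the repair is to bring section 9 into line with it.

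**What to change.** 1. Either add the existing DD+90 user-friendliness and need-for-nurses items to the DD+30 visit, or limit that part of the section 2.2 objective to DD+90. The first uses existing items at an existing visit and costs a small extra patient burden. The second is wording only, and gives up the DD+30 opinion comparison.
2. Name the visit or visits for the ease-of-use test in section 13.4.3. This is wording only.
3. Restate the economic comparison as an independent-groups comparison between the two arms over the same follow-up period. A t-test on means would serve. This is wording only.
4. State where the number of nurse visits and the costs come from, or drop these supplementary analyses. If no count is yet recorded, one entry on the existing weekly self-questionnaire would supply it, again with a small patient burden; the cost source would still have to be named.

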3. ETHICAL GUARANTEES OF THE TRIAL

This trial, carried out in accordance with Good Clinical Practice, received a favorable opinion from the Committee for the Protection of Persons (CPP) "IDF 11" (see Annex 3 §16.3).

After receiving complete information about the circaid® compression system, the other products used as comparators and the conditions for carrying out the study, each patient will give their written consent on a form in 3 copies: the original for the patient, a first copy for the investigator, a second copy for the sponsor (submission in a sealed envelope) (see Annex 4 §16.4). The patient is free at any time to stop her participation in the study.

4. NATURE OF THE TRIAL

Controlled randomized open label clinical trial on two parallel groups.

5. PATIENTS SELECTION

All patients meeting all inclusion criteria and none of the non-inclusion criteria will be eligible for the study.

5.1. INCLUSION CRITERIA

To be included in the trial, patients will:

- be women over the age of 18;
- presenting a unilateral lymphedema of the upper limb of stage II or III according to the International Society of Lymphology, secondary to the curative ganglion treatment of a cancer, whatever its nature, and requiring a decongestive treatment by contention / compression;
- presenting an increase in the volume of the arm affected by lymphedema of at least 10% when compared to the contralateral arm;
- benefiting of the French health insurance coverage;
- duly informed of the benefits, constraints and risks of the study;
- medically and legally able to understand the methods of carrying out the study and to give written informed consent to participate in the study;
- having given their free written informed consent to their participation in the study.

5.2. NON-INCLUSION CRITERIA

Not be included in the study:

- from a medical point of view, the patients:
 - with stage I lymphedema;
 - with lymphedema of multiple locations;
 - having had intensive decongestive treatment in the last 6 months;
 - having a recurrence of cancer or a peripheral arterial disease contraindicating or restraining compression.
- from a legal point of view, the patients:
 - not in a position to give free and informed consent because of an administrative or judicial decision or a pathology that may affect their judgment or a difficulty of linguistic comprehension;
 - currently participating in another clinical trial or in an exclusion period from another clinical trial;
 - who may not adhere to the terms of the protocole.

